COVER PAGE

The Dedicated African American Dad Study

NCT number-NCT02412748

Document date- July 15, 2016

Study Protocol & Statistical Analysis Plan

Overall Study Design

The study was a randomized clinical trial comparing the effects of a 12-week, 9-session fatherhood intervention, Building Bridges To Fatherhood (BBTF), to an attention control Financial Literacy Program (FLP) for AA non-resident fathers. Both conditions had a booster session at 18 weeks. At the booster session, the BBTF intervention group met to problem-solve around remaining challenges to positive father involvement and to refresh the content offered during the 12-week program. The attention control FLP condition met to discuss progress towards acquiring financial literacy, but without mention of fatherhood or father involvement. AA non-resident fathers were randomly assigned to the two conditions. This study used a block randomization procedure to facilitate equitable distribution of fathers into the BBTF and FLP conditions. Data collection began in study year 2 and continued for 2 years. During each wave's 12 weeks of recruitment, there were six blocks with four participants in each block. Each block was constructed with an equal number of BBTF and FLP assignments. Data collection was done at baseline, immediately post intervention (12 weeks), and 3 months post intervention (24 weeks).

The BBTF sessions and FLP control sessions were held at community colleges or community neighborhood sites. The study was conducted in a series of 6 waves over 96 weeks, alternating from westside sites southside sites over 96 weeks. Each wave began with 12 weeks of recruitment at community locations in proximity to the site. After the intervention and control groups had been recruited at each site, the two conditions began in parallel. The BBTF intervention and FLP control groups met on different nights and in different locations at the facility in order to minimize contamination. Once the groups began at one site, recruitment began for the next wave that was to be conducted at the alternate site. This design minimized historical contamination within a site because of the 12-week hiatus between the beginning of one series of groups and the end of the previous groups.

Subjects and Setting

Inclusion Criteria. Inclusion criteria were: (1) AA biological father of a child 2 to 6 years old; (2) child lived with father no more than 48 hours per week (e.g., spends the weekends with his or her father); and (3) the child lived with the biological mother (or other custodial relative such as grandmother) in the metropolitan Chicago area. These fathers are referred to as AA non-resident fathers. Additional criteria included: (1) child's mother willing to consent to complete the child assessments--[this criterion was amended in order to allow fathers access to program content even when mothers were unwilling to complete research measures]; (2) child's mother amenable to facilitating opportunities for fathers to interact with their children in order to practice skills learned in the program; and (3) father able and willing to travel to one of two intervention sites to attend a weekly program. The study was limited to fathers with a target child aged 2-6 years. The rationale for this limit was based on the developmental phase when families are most vulnerable to decreased father involvement and children are highly dependent on parenting for their growth and development.

Exclusion criteria included: (1) fathers with histories of child abuse, neglect, or violence perpetuated against the child or the child's mother (based on mother or father report).

The city of Chicago is composed of 77 community areas identified by numbers. We recruited fathers from the approximately 171,000 AA men between the ages of 18 and 65 residing in 13 predominantly AA (73-98%) community areas. These mostly low-income community areas (median income \$13,596-\$43,728), with 23% to 55% of incomes below poverty level. Based on data that reveals that more than two-thirds of AA children live in homes without their biological fathers,^{1,2} we are confident that the communities will serve as rich recruitment sites for AA non-resident fathers. We identified two conveniently located sites to conduct the programs, one located on Chicago's West Side and the other located on Chicago's South Side.

Power Analysis. Previous research¹⁰⁷ suggests that an intervention that is similar to BBTF could produce an improvement in father engagement ($d = .42$).¹⁰⁸ Assuming an effect size of $d = .42$, a one-tailed alpha of .05, and a sample size of 144 participants (72 per group), we obtained a power of .80 for this design. Assuming a 20% dropout rate, the total sample needs to be 180 participants, 90 per group.

Sample Recruitment. Three recruiters, ethnically matched to the participants and with ties to the community, were trained in minority outreach by the research team to establish relationships with fathers that supported recruitment. They were also trained to give presentations about the program to community groups. It was essential that the data collectors hired were comfortable in low-income communities, highly personable, and very patient (particularly when parents failed to show up for appointments). All program advertisements included a brief description of a self-improvement program for AA fathers, featured photographs of scenes of fathers meeting together, and provided a number to call and e-mail address for further information. We continued with the highly successful active (recruiters meet directly with potential participants) and passive (potential participants are prompted to contact the staff) recruitment strategies used in our extensive prior work in low-income Chicago communities.^{95,104,105} Recruiters met with key informants already identified from churches, barbershops, community centers, schools, day care centers, local business establishments, dry cleaners, and sports venues to obtain the anticipated broad reach. Key informants were given brochures/flyers to pass on the information to potential participants. In addition, notices were placed in church bulletins and community newspapers. Active strategies included giving presentations at community churches and other community gathering places.

Fathers who meet inclusion criteria were informed that half of the fathers in the study would be randomly chosen to participate in the intervention group or the control group. Fathers had to agree to this procedure. After informed consent was obtained and baseline measures were completed, randomization took place. Block randomization assignments were kept in sealed envelopes in the research office in the order in which they were generated and then communicated by the project director to the data collector via text message, who was blind to the assignment prior to consenting and enrollment. The intervention and control groups began simultaneously at the end of the 12-week recruitment period.

Sample Retention. We continued with the successful strategies that resulted in 80% retention in prior community-based studies.^{47,106} First, the sessions were offered at two sites convenient to public transportation and with free parking. Participants were reimbursed for the cost of public transportation for coming to and from the study sites for the sessions and data collections (round-trip public transit card or \$10 gas card). They received a \$40 gift card after completing each of the three data collections. At the sessions, they were given a healthy drink and snack. Three times during the BBTF program (Weeks 4, 8, and 12), there were no scheduled session. To enhance fathers' opportunities for spending time with their child and serve as a motivator for continued involvement in the BBTF program, they were given a \$30.00 activity voucher for these weeks. Our prior work with fathers suggested that this was a retention strategy that was highly valued by AA fathers who were often seeking opportunities and resources for spending fun, engaging, and educational time with their children.^{9,47,109} We identified multiple means of remaining in contact with fathers including: work, home, and cell phone numbers; noted if they accepted text messages; home and e-mail addresses; and the contact information of three friends, relatives, or coworkers who would know how contact them should their phone service be terminated or mailing address change. Fathers received two reminder telephone calls, text messages, or e-mails two days prior to and the day of each group session and data collection. Fathers were given the opportunity to have the baseline, 12- and 24-week data collections either at the community college or another location of their choosing, such as their homes.

Mothers received a \$40 gift card for completing child outcome and father involvement assessments. Data collection for the mothers at baseline, 12 and 24 weeks was conveniently conducted via phone administration, mailed paper-and-pencil survey or online via SurveyMonkey (based on the mother's preference). Our intent was to ensure that the process of collecting data from the mother was not overly burdensome. Contact information was obtained as with the father.

Procedures

Fathers were given an explanation of the study in person or over the phone. This included informing them that half of the fathers in the study would be randomly chosen to participate in the intervention group and half in the control group. Fathers who were interested gave verbal consent to be screened for eligibility criteria. Fathers were also: (1) asked for the mother's contact information (home phone, work phone, cell phone, and e-mail), (2) provided a letter to give the child's mother informing her of the study and asking her to contact us within one week if not interested in participating. All mothers who did not contact us were contacted for consent and data collection. If mothers were interested, arrangements were made to meet them at a place of their convenience (e.g., their home, work, community gathering place). Mothers were also given the opportunity to complete data collection via telephone interview. The father's written consent was obtained at first contact (if in person), or we scheduled to meet at a place of his convenience. These consent strategies were successfully used in preliminary study. After obtaining fathers' and mothers' written consent, baseline measures were administered. Baseline father questionnaires were father outcomes, paternal involvement, father-mother relationship quality, and child outcomes. Baseline mother questionnaires were child outcomes, paternal involvement, and father-mother relationship quality. Fathers were then assigned to one of the two conditions. Fathers in both conditions participated in three 3-week sessions, each of which was followed by a break week (total of 12 weeks); and participated in a booster session at 18 weeks. The BBTF and FLP were held at the community colleges or other their community (South or West Side of Chicago) with two trained group leaders. A cohort of 12-15 fathers will be assigned to each condition. The program sessions for both conditions begin with a greeting, a healthy snack, and the introduction of their respective program material. Data collection occurred again at 12 and 24 weeks. They received reminder calls two to three times in the week before each of the nine program sessions, the booster session, and the three data collections (baseline, 12, and 24 weeks). Fathers received a \$40 gift card and mothers received a \$40 gift card at baseline, 12, and 24 weeks for completion of measures administered at those times.

Data Analysis Data analysis is described with respect to the three specific aims and hypotheses that were tested. Missing data was imputed using SAS Proc MI, a multiple imputation computer program based on the work of Rubin.¹³¹ All continuous data was examined for statistical normality. Histograms were obtained for these variables, and skew and kurtosis were assessed in order to assess statistical normality. Where possible, we normalized these data using Tukey's ladder of transformation¹³² before conducting statistical analysis. SPSS for Windows (Version 11) and SAS (Version 9.1) was used for data management and statistical analysis. A two-tailed 0.05 significance level was used for all statistical tests except where noted below. All analyses were performed on an intent-to-treat basis. Outcome measures that could be successfully transformed to achieve normality were in all likelihood close enough to a normal distribution that the robust nature of the F-test made it possible to obtain reasonable p values in the study.

Descriptive statistics on the sample data for all research variables were obtained. In addition, one-way ANOVAs and chi-square analysis on the demographic and baseline research measures were performed between the intervention and control groups to determine that they

were comparable. The effects of participant attrition on the research variable were also assessed using one-way ANOVAs.

Hypothesis 1: Relative to the attention control condition, BBTF program fathers will report better father outcomes (psychological well-being, parenting competence, and father-mother relationship quality) and greater paternal involvement (material support, in-kind support, father-child interaction) at 12 weeks and 24 weeks.

Data analysis were a repeated measures analysis of variance (RM-ANOVA) to address Hypothesis 1. The basic design for these analyses was a 2x3 design with three assessment time points (the within-subjects factor) crossed with the two treatment conditions (BBTF and the comparison group [the between-subjects factor]). The null hypothesis for all these analyses was that changes for all dependent measures (psychological well-being, parenting competence, father-mother relationship quality, material support, in-kind support, and father-child interaction) would remain constant for the two groups over time. The alternative hypothesis was that they would increase over time in the BBTF group relative to the control group. This was the interaction effect in the RM-ANOVA. An initial multivariate analysis was be conducted first to see if there was any overall effect. If the null hypothesis was rejected in the multivariate analysis, we examined the univariate analyses. We tested for violations of sphericity, and if they were in evidence, then a Greenhouse-Geisser correction was used to estimate probability values.

In order to determine when these changes occurred across the three assessment time points, a follow-up analysis was conducted with time reparameterized into a set of two orthogonal Helmert contrasts. The two contrasts were of the form (1, -1/2, -1/2; 0, 1, -1), where if the first contrast was significant, this indicated that the critical differences occurred between times 1 and 2; and if the second was significant, the changes took place between times 2 and 3. This informed us as to the transition point or points where the velocity changes were greatest between the treatment and comparison groups.

Hypothesis 2: Across both conditions, father outcomes and post-intervention ratings of father-mother relationship quality will mediate paternal involvement at 12 weeks and 24 weeks.

This analysis used a regression approach to mediation analysis, as that described in MacKinnon, 2008.¹³³ This approach looked at the extent to which changes in paternal involvement over time were explained by changes in the father outcomes and the mother-father relationship in both the treatment and control groups. This effect was estimated using a series of three regression analyses. The dependent variable (a measure of paternal involvement) at Time 2 (12 weeks) was regressed on a dummy-coded treatment variable and the same paternal involvement measure at Time 1 (baseline). Then the mediators (father outcomes and mother-father relationship) were included in the regression models, and the change in R-squared was used to determine their impact. These analyses were repeated for Times 1 and 3 (24 weeks).

Hypothesis 3a: Relative to the attention control group, BBTF children will have improved child outcomes (behavioral, emotional, and social) at 12 weeks and 24 weeks.

The analysis of Hypothesis 3a was directly parallel those described for Hypothesis 1. The only difference was in the dependent measures, which were be child outcomes instead of paternal involvement outcomes.

Hypothesis 3b: Across both conditions, father outcomes, father-mother relationship and paternal involvement will mediate child outcomes at 12 weeks and 24 weeks.

This analysis used the same regression approach to mediation analysis described in Hypothesis 2, with the only differences being that the outcome variable was the child outcomes

rather than paternal involvement; paternal involvement acted as a mediator along with father outcomes and father-mother relationship.

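### The block schedule provides for 144 randomised fathers, the number the power section needs after dropout, not the 180 it says must be enrolled

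*Combined protocol and SAP*

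**What the plan says.** The Overall Study Design section describes the randomisation in blocks. Within each wave's 12-week recruitment period "there were six blocks with four participants in each block", each split equally between the fatherhood programme and the financial literacy control. The same section says: "The study was conducted in a series of 6 waves over 96 weeks".

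The Power Analysis paragraph, under Subjects and Setting, assumes d = .42 and a one-tailed alpha of .05, and reports that with "a sample size of 144 participants (72 per group), we obtained a power of .80 for this design". It then allows for 20% dropout and concludes that "the total sample needs to be 180 participants, 90 per group". The Sample Retention paragraph supports that dropout rate by citing "successful strategies that resulted in 80% retention in prior community-based studies".

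Two other statements bear on the point. Procedures says: "A cohort of 12-15 fathers will be assigned to each condition". Data Analysis says: "Missing data was imputed using SAS Proc MI", with all analyses by intention to treat.

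**The concern.** The schedule and the power section give different numbers of fathers to be randomised. The schedule's total equals the number that the power section wants to have left once dropouts have gone, both overall (144) and per group (72). That is what one would see if the blocks had been laid out from the figure before inflation for dropout.

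The number randomised is a basic design quantity. As the document stands, a reader cannot tell whether a final count of 144 would mean full enrolment or a shortfall of 36, which is 20% of the target. If the schedule is what was followed, the stated power of .80 holds only if dropout costs no information, although the plan itself expects to lose one father in five.

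**Working it through.** **Inputs.** From Overall Study Design: 6 blocks per wave, 4 fathers per block, 6 waves, 1:1 allocation within blocks. From Power Analysis: d = .42, one-tailed alpha .05, 144 fathers (72 per group) for power .80, 20% dropout, 180 to be enrolled. From Procedures: 12 to 15 fathers per condition.

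**1. The plan's own figures reproduce.** For a two-sample t-test with n per group, power comes from the noncentral t distribution with 2n − 2 degrees of freedom and noncentrality d × √(n/2). At n = 72 the noncentrality is .42 × √36 = 2.52 with 142 degrees of freedom, and one-tailed power is .806, which agrees with the stated .80. The inflation for dropout is 144 / (1 − .20) = 180, as stated.

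**2. What the block schedule delivers.**
- Per wave: 6 × 4 = 24 fathers, 12 per condition.
- Over six waves: 24 × 6 = 144 fathers in 36 blocks, 72 per condition.
- Shortfall against the target: 180 − 144 = 36.

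**3. What 180 would need.** 180 / 4 = 45 whole blocks, against 36 scheduled. Block size is therefore not the obstacle; the number of blocks per wave is. Spread evenly, 180 is 30 fathers per wave, or 7.5 blocks, so the waves could not all be the same size.

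**4. Whether the cohort size settles it.** Reading 12 to 15 as per condition per wave, which is an inference, the range is 12 × 2 × 6 = 144 to 15 × 2 × 6 = 180. It covers both totals. Six balanced blocks of four give exactly 12 per condition per wave, so 13 to 15 cannot come from the schedule as described.

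**5. Whether extra waves could fill the gap.** At 24 per wave, 180 needs 180 / 24 = 7.5 waves. Six consecutive 12-week recruitment periods take 72 weeks, and 24 weeks of follow-up for the last wave brings this to 96. The stated calendar is already full.

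**6. Power if 144 were randomised.** Same test and assumptions as in step 1, completers only:

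| Dropout | n per group | Noncentrality | One-tailed power |
|---|---|---|---|
| 0% | 72 | 2.52 | .806 |
| 10% | 64.8 | 2.39 | .768 |
| 20% | 57.6 | 2.25 | .724 |
| 30% | 50.4 | 2.11 | .673 |

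At 20% dropout the number left is 144 × .80 = 115.2. The effect detectable with power .80 rises from d = .416 at 72 per group to d = .466 at 57.6 per group.

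**The case against.** The best defence starts from the cohort size in Procedures. Read per wave, its two ends give exactly 144 and 180, so the plan evidently had the larger total in view, and the six blocks might describe only the lower end of a recruitment range. It is also true that 144 is nowhere stated as a number randomised; it is the product of two statements. This shows that an allowance for dropout was contemplated. It does not reconcile the text: no section says that further blocks could be opened, and six blocks of four cannot place a thirteenth father in a condition.

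A second objection is that the loss of power is conditional. It assumes that 144 were randomised and that dropouts contribute nothing. The plan intends multiple imputation, intention-to-treat analysis and a repeated-measures interaction test, whose power depends on within-person correlations that the document does not give. These limits stand, and .72 is the end of the range at which imputation recovers nothing. It is still the fair figure to set beside the plan's .80, because that .80 reproduces as a two-sample t-test and the inflation to 180 itself counts dropouts as lost. Imputation also does not change how many fathers the schedule randomises.

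A third objection is that the mismatch leaves the 1:1 allocation, the treatment comparison and the type I error untouched. That is correct. What it affects is the planned size and the stated power.

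**Conclusion.** The concern holds. The document gives two incompatible planned totals, 144 by the block schedule and 180 by the power section, and no statement reconciles them. This rests only on figures in the document.

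The consequence for power is conditional on 144 having been randomised. With the plan's own 20% dropout, power on the test that reproduces its calculation lies between .72 (imputation recovers nothing) and .81 (it recovers everything). The planned repeated-measures test may differ. Because the number randomised is not reported, this is an inconsistency in the design and not evidence that the trial under-enrolled. Whether a one-tailed test is appropriate is a separate question and plays no part here.

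**What to change.** State one total and the matching number of blocks, and bring Overall Study Design, Power Analysis and Procedures into line with it.

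- **If 180 is the target:** state 45 blocks of four. One arrangement is three waves of 7 blocks and three of 8: 3 × 7 × 4 + 3 × 8 × 4 = 84 + 96 = 180. That gives 14 or 16 fathers per condition per wave, so the 12 to 15 in Procedures must be restated. If randomisation is still open, each 12-week recruitment period must reach 30 fathers on average instead of 24, which is 25% more. This asks for nothing beyond the 180 that the power section already requires.
- **If 144 is the true number, or randomisation has finished there:** state 144 randomised, about 115 expected completers and one-tailed power of about .72 under the plan's assumptions, noting that imputation may recover part of the loss. This is a change of text only, at the price of a less favourable stated power.

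The mostly past tense of the document suggests that randomisation may be complete. In that case only clarification or restatement is possible, and reporting the number actually randomised would settle which total applies.

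### Wave, the stratum within which fathers are randomised, is left out of every model; it belongs there with wave-by-visit, alongside a session-group effect, and the net direction of the standard-error error is unknown

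*Combined protocol and SAP*

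**What the plan says.** **Randomisation** (Combined protocol and SAP, Overall Study Design). Assignments are generated wave by wave: "During each wave's 12 weeks of recruitment, there were six blocks with four participants in each block", and "Each block was constructed with an equal number of BBTF and FLP assignments". On waves and sites: "The study was conducted in a series of 6 waves over 96 weeks, alternating from westside sites southside sites over 96 weeks". Each wave therefore sits in one area and is balanced between conditions by design.

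**Delivery** (Overall Study Design; Procedures). The two conditions of a wave run in parallel but meet separately, on different nights, with two leaders per group. On group size: "A cohort of 12-15 fathers will be assigned to each condition".

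**Analysis** (Data Analysis, Hypothesis 1). The model is stated as follows: "The basic design for these analyses was a 2x3 design with three assessment time points (the within-subjects factor) crossed with the two treatment conditions". The hypothesis is tested through the condition-by-time term: "This was the interaction effect in the RM-ANOVA". Hypothesis 3a uses the same model with child outcomes. The regressions for Hypotheses 2 and 3b contain a treatment indicator, the baseline value of the outcome and the mediators. No model has a term for wave, site or session group.

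**The concern.** An analysis should normally reflect the groups within which it randomises. When assignment is balanced within a stratum, differences between strata do not affect the comparison of the two conditions. If the stratum is not fitted, those differences still count as error, so the test is conservative and some power is lost. Here the waves span 96 weeks and two parts of the city, so some variation between them is plausible.

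The omission also bears on any later correction for group delivery. A random effect for session group (wave x condition) without a wave term treats the two parallel groups of one wave as unrelated and leaves what they share in the error.

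**Working it through.** **1. The plan's own figure.** Power Analysis gives d = 0.42, one-tailed alpha .05, 72 per group, power .80. Normal approximation: Φ(0.42 × √(72/2) − 1.645) = Φ(2.52 − 1.645) = .809. The required size is 71 per group, and 144/0.8 = 180. The stated figures reproduce. At the two-tailed .05 that Data Analysis sets as the default, power is Φ(2.52 − 1.96) = .712.

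**2. Structure.** 6 blocks × 4 = 24 fathers per wave, 12 per condition. 6 waves × 2 conditions = 12 session groups. 144/12 = 12 and 180/12 = 15, which matches the stated cohort size. Area is constant within a wave, so six wave levels absorb site.

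**3. Which variance counts.** The tested effect is a contrast within father, such as the mean of the follow-ups minus baseline. A wave or site effect that is the same at all three visits cancels. Only wave-by-time variation remains. A simulation (20,000 runs, 6 waves × 12 per condition) agrees: with constant wave effects the model standard error is 0.118 with or without a wave term.

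**4. Omitted wave, taken alone.** Let w be the share of the change contrast's variance that wave explains. The documents do not give it, so a range is assumed. The standard error without wave, relative to that with wave, is 1/√(1 − w). Power with wave fitted is Φ(2.52/√(1 − w) − z), with z = 1.645 one-sided and 1.96 two-sided.

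| w | SE too large by | Two-sided type I error | Power, one-sided | Power, two-sided |
|---|---|---|---|---|
| 0 | 0 | .050 | .809 | .712 |
| 2% | 1.0% | .048 | .816 | .721 |
| 5% | 2.6% | .044 | .827 | .734 |
| 10% | 5.4% | .039 | .844 | .757 |

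Type I error is that of the model without wave. Power is that with wave fitted. By noncentral t, with 5 degrees of freedom removed, two-sided power goes from .706 to .715, .728 and .751.

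**5. Session groups push the other way.** Let g be the session-group share of the same variance (also assumed). The true variance of the difference is 2[(1 − w − g)/72 + g/6], against about 2/72 in the plan's model. The ratio is 1 − w − g + 12g = 1 − w + 11g.

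- With w = 0 this is the usual design effect. The true standard error exceeds the model's by about 5%, 10%, 24% or 45% at g = .01, .02, .05 or .10.
- The plan's standard error is too large on balance only if 11g < w. For w = 2%, 5% or 10%, that means g below about 0.18%, 0.45% or 0.91%.
- With w = 5% and g = 2%, the ratio is 1 − .05 + .22 = 1.17, its root is 1.082, and type I error is 2[1 − Φ(1.96/1.082)] = .070. With wave fitted alone, the ratio is about 1.17/.95 = 1.232, its root is 1.110, and type I error is about .077. Simulation gives about .07 and .08, and about .05 with wave and session group both fitted.

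**6. Session-group analysis without and with wave.** Simulation of the 12 group means: g = 2%, d = 0.42, two-sided .05. The condition test has 12 − 2 = 10 degrees of freedom without wave and 10 − 5 = 5 with it.

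| w | Type I error, without / with wave | Power, without / with wave |
|---|---|---|
| 0 | – | .54 / .45 |
| 2% | .035 / .049 | .47 / .46 |
| 5% | .023 / .050 | .39 / .47 |
| 10% | .011 / .050 | .29 / .49 |

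**7. Regressions for Hypotheses 2 and 3b.** The baseline value removes stable wave differences only in part. With an assumed stable wave share of 5-15% and a within-wave baseline correlation of .3-.5, simulation leaves the standard error of the treatment coefficient about 0.6-3.3% too large. The mediators are not randomised, so balance within wave gives no direction for the R-squared-change test.

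**The case against.** The strongest case against the point has three parts.

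1. The primary test is within father, so differences in outcome level between waves or areas, which are the plausible ones, drop out. Percentages based on the wave share of outcome level would describe the wrong variance. This stands. The figures in the working apply only to the change contrast, and the documents give no reason to expect any particular amount of wave-by-time variation.

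2. Even then the gain is small: at a 5% share, two-sided power moves from .706 to .728. This also stands, and it limits the point to an improvement.

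3. A reader might infer that, because a balanced stratum is omitted, the trial's standard errors are too large and its tests err on the safe side. The documents do not support that. Both conditions are delivered in separate groups and the model treats fathers as independent. A session-group share well under 1% is enough to reverse the sign, and wave fitted alone then makes type I error worse (about .08 against .07).

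The objection does not remove the case for wave itself. Once clustering is handled, as the delivery format requires, leaving wave out can make the test strongly conservative (type I error .023 or .011 at 5% or 10%), while the model with wave stays near .05 in the scenarios run. The two terms answer different problems and are needed together.

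**Conclusion.** The point holds as a cheap improvement. The trial randomises within wave, and none of its models contains wave. The separate effect of that omission on the condition-by-time test is modest conservatism, and it vanishes if waves differ only by a constant level. For the mediator tests no direction can be given.

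The net error in the plan's standard errors is unknown in sign. With 12 fathers per group, clustering dominates as soon as the session-group share exceeds about one eleventh of the wave share, so standard errors that are too small are the more serious risk.

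The wave shares, session-group shares and simulation settings are all assumptions. What rests on the documents is the structure: six waves, 1:1 blocks within wave, separate groups of 12-15, and a model with condition and time only.

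**What to change.** - **Hypotheses 1 and 3a:** add wave as a six-level factor (it absorbs site) with wave-by-visit. For the condition-by-time test, wave-by-visit is the term that matters.
- **Hypotheses 2 and 3b:** add wave as a covariate.
- **In all of these models:** fit wave together with a random effect for session group (wave x condition), using small-sample degrees of freedom. In the repeated-measures models, let that effect act on the follow-up visits, since the groups do not exist at baseline. Do not add wave in place of the session-group effect.

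Wave is set at recruitment for every father, so no new data are needed. At father level the cost is 5 degrees of freedom (142 to 137 with 144 fathers). Once session group is modelled it is 5 of 10 group-level degrees of freedom, so the change is not free: at a 2% session-group share it breaks even when wave explains about 2% of the contrast's variance, and it lowers power from .54 to .45 if wave explains nothing.
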